5.4.2 Supportive Care Guidelines – General Medications

The following treatments are permitted throughout the duration of the study treatment phase and during follow-up:

- Standard therapies for pre-existing medical conditions unless listed as prohibited therapy below. Any medication intended solely for supportive care (e.g., analgesics, antidiarrheal, anti-depressants) may be used at the investigator's discretion.
- Anti-diarrheal medications should not be administered prophylactically before initial treatment with study drugs. At the discretion of the investigator, prophylactic antiemetic and anti-diarrheal medication(s) may be used as per standard clinical practice before doses of study drugs.
- Hematopoietic growth factors (e.g., G-CSF, granulocyte macrophage colony stimulating factor) may be used at investigator's discretion for the primary prophylaxis and/or management of treatment-emergent neutropenia and/or for secondary prophylaxis as per NCCN/European Society for Medical Oncology guidelines ^{47, 48} or local standard practice.
- Bisphosphonate or denosumab therapy to be used in accordance with the approved labeled indication and/or nationally recognized treatment guidelines. Participants already receiving bisphosphonate/denosumab at the time of study entry can continue the treatment.
- Anticoagulants - Anticoagulation with heparin, heparin derivatives, and/or warfarin, and/or NOAC's may be given at the discretion of the treating physician.
- Pain medications administered per standard clinical practice are acceptable while the participant is enrolled in the study.
- Participants who experience toxicities should be treated symptomatically as clinically indicated. Medications that are considered necessary for the participant's welfare and that are not expected to interfere with the evaluation of study treatment or be restricted may be given at the discretion of the investigator. Ancillary treatments will be given as medically indicated.

5.5 Duration of Therapy

Duration of therapy will depend on individual response, evidence of disease progression and tolerance. In the absence of treatment delays due to adverse event(s), treatment may continue for 2 years or 35 cycles of therapy or until one of the following criteria applies:

- Disease progression in any participant who showed first radiologic evidence of progressive disease (PD) by RECIST 1.1 (see Section 11.1.4) and is deemed clinically stable, it is at the discretion of the investigator to continue treating the participant until progression is confirmed at least 4 weeks from the date of the first radiologic evidence of PD. Further details are described below.
- Intercurrent illness that prevents further administration of treatment
- Unacceptable adverse event(s) which include the following (see also section):
 - Any Grade 2 drug-related uveitis or eye pain or blurred vision that does not respond to topical therapy and does not improve to Grade 1 severity within the re-treatment period OR requires systemic treatment
 - Participants requiring > two dose delays for the same type of event should be removed from protocol
 - Any adverse event, laboratory abnormality, or intercurrent illness which, in the judgment of the investigator, presents a substantial clinical risk to the participant with continued study drug dosing
 - Any dosing interruption lasting >5 weeks, with the following exceptions:
 - Participants being tapered after high dose corticosteroids over one month followed by a two-week observation period will be allowed an additional two weeks to restart treatment (a maximum eight-week interruption).
 - Dosing interruptions >5 weeks that occur for non-drug-related reasons may be allowed if approved by the Investigator. Prior to re-initiating treatment in a participant with a dosing interruption lasting >5 weeks, the PI must be consulted.
 - Grade 2 pneumonitis requiring steroids.
 - Grade 3 or Grade 4 drug-related autoimmune or inflammatory events including uveitis, pneumonitis, diarrhea, colitis, neurologic adverse events, hypersensitivity reaction, or infusion reaction of any duration requires discontinuation except as noted below:
 - Any other grade 3 non-skin, drug-related AE lasting >7 days including fatigue.
 - Any grade 3 or 4 drug-related laboratory abnormality or electrolyte abnormality, not associated with underlying organ pathology, that does not require treatment except for electrolyte replacements **does not** require treatment discontinuation.
 - Grade 3 amylase or lipase abnormalities that are not associated with diabetes mellitus (DM), associated liver or gall bladder inflammation clinical manifestations of pancreatitis and which decrease to < Grade 2

within 1 week of onset **may** resume study treatment when resolved.

- Any grade 4 events except as noted above.
- Any participants who require additional immune suppressive treatment beyond steroids should go off study treatment
- Participant demonstrates an inability or unwillingness to comply with the medication regimen and/or documentation requirements
- Participant decides to withdraw from the protocol therapy
- General or specific changes in the participant's condition render the participant unacceptable for further treatment in the judgment of the treating investigator

Participants will be removed from the protocol therapy when any of these criteria apply. The reason for removal from protocol therapy, and the date the participant was removed, must be documented in the case report form (CRF). Alternative care options will be discussed with the participant.

In the event of unusual or life-threatening complications, treating investigators must immediately notify the Overall PI, [name], MD.

Confirmation of Progressive Disease

Pembrolizumab, like other immunotherapeutic agents, may produce antitumor effects by potentiating endogenous cancer-specific immune responses. The response patterns seen with such an approach may extend beyond the typical time course of image responses seen with cytotoxic agents, and can manifest as a clinical response after an initial increase in tumor burden or even the appearance of new lesions.

For any participant who shows first radiologic evidence of progressive disease (PD) by RECIST1.1 (see Section 11.1.4) and is deemed clinically stable, it is at the discretion of the investigator to continue treating the participant until progression is confirmed at least 4 weeks from the date of the first radiologic evidence of PD. If progression is confirmed, the participant will be discontinued from study treatment. If progression is not confirmed on the subsequent scan, the participant should continue to receive study treatment and have radiographic scans performed every 6 weeks if the participant has been on study for less than 24 weeks, or every 9 weeks for participants who have been on study greater than 24 weeks to monitor disease status. Any participant who had initial radiologic progression and is deemed clinically unstable should be discontinued from both study drugs and no subsequent scan for confirmation is required. Exceptions may be considered to continue treatment in the presence of clinically stable or improved condition only after consultation with the PI.

For purposes of PFS assessment on this trial, in addition to radiographic assessment of tumor response or progression, the investigator should take into account the clinical condition/stability of participants. Clinically stable is defined by the following criteria:

- Absence of signs and symptoms (including worsening of laboratory values) indicating disease progression

- No decline in ECOG performance status
- Absence of rapid progression of disease
- Absence of progressive tumor(s) at critical anatomical sites (eg, cord compression) requiring urgent alternative medical intervention

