5.8 Criteria to Resume Treatment after a pembrolizumab related iAE

Management of adverse events is summarized in section 6 and may include holding of pembrolizumab, and/or the use of steroids for the management of immune related AEs. If pembrolizumab is held for toxicity, participants are permitted to continue protocol therapy with eribulin. Eribulin can be continued during corticosteroid treatment.

If drug administration is held until the next scheduled time point, please continue to count weeks/doses. If participants must be delayed due to toxicity, all assessments can be obtained with the modified treatment dose schedule as noted in this section.

Pembrolizumab may be interrupted for situations other than treatment-related AEs such as medical / surgical events or logistical reasons not related to study therapy. Participants should be placed back on study therapy within 8 weeks of the scheduled interruption, unless otherwise discussed with the Sponsor. The reason for interruption should be documented in the participant's study record.

Restarting pembrolizumab may be considered in participants who experience grade 2 events and some grade 3 events (skin rash and thyroiditis). Because of this, stopping treatment and starting steroids earlier, as per section 6, to obtain resolution with the possibility for restarting rather than waiting for higher grade events is encouraged.

For non-autoimmune or non-inflammatory events, participants may resume treatment with study drug when the drug-related AE(s) resolves to Grade ≤ 1 or the baseline value, with the following exceptions:

- Evaluation to exclude any additional immune mediated events (endocrine, GI, and liver / pancreas function) as clinically indicated must be made prior to restarting. [SEP]
- Non-drug-related toxicity including hepatic, pulmonary toxicity, diarrhea, or colitis, must have resolved to baseline before treatment is resumed. [SEP] If the criteria to resume treatment are met, the participant should restart treatment no sooner than the next scheduled time point per protocol. However, if the treatment is delayed past the next scheduled time point per protocol, the treatment should resume at the earliest convenient point [SEP] that is within the five-week delay period.

For participants treated with corticosteroids:

For participants treated with high dose steroids with pembrolizumab, toxicity must resolve to baseline within 8 weeks of treatment.

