Participants should be off steroids for at least 2 weeks with no recurrence or new events. New immune related events or exacerbation of existing events during steroid treatment or taper suggest the presence of ongoing immune activation and should require permanent discontinuation of pembrolizumab.

Grade 2 events must resolve to grade < 1 or baseline before considering retreatment.

All participants treated with steroids for grade ≥ 2 events should have pembrolizumab held until resolution to grade < 1 for at least 2 weeks following complete removal from steroid treatment except for maintenance replacement doses for adrenal insufficiency (preferably no greater than 10mg prednisone equivalent daily).

All participants treated with steroids for grade ≥ 3 events should have pembrolizumab discontinued. Participants with grade 3 thyroiditis and skin rash may continue therapy as for grade 2 events with resolution and stable replacement treatment.

Participants with hepatitis, pancreatitis, pneumonitis, and colitis are at risk for exacerbation with retreatment if there is residual inflammation and should resolve to Grade 0 or baseline before retreatment. Baseline can mean the initial grade *i.e.* grade ≤ 1 where permitted on study.

Participants with thyroiditis or hypopituitarism who are stable as above may be restarted with replacement hormones including thyroid hormone and physiologic doses only of corticosteroids. Please note that hypophysitis with symptoms of headache, visual or neurologic changes or radiologic evidence of pituitary enlargement and other CNS events such as aseptic meningitis or encephalitis should be considered grade 3 events.

Prior to starting corticosteroids or hormone replacement for any reason, appropriate endocrine testing including cortisol, ACTH, TSH and T4 must be drawn if clinically feasible to document baseline function and distinguish the pituitary from peripheral organ dysfunction and later from steroid (or thyroid) treatment associated ACTH (or TSH) suppression. Steroids should be started prior to obtaining results based on clinical indications.

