6. DOSING DELAYS/DOSE MODIFICATIONS

Dose delays and modifications will be made as indicated in the following table(s). The descriptions and grading scales found in the revised NCI Common Terminology Criteria for Adverse Events (CTCAE) version 5.0 will be utilized for dose delays and dose modifications. A copy of the CTCAE version 5.0 can be downloaded from the CTEP website http://ctep.cancer.gov/protocolDevelopment/electronic_applications/ctc.htm.

Dosing interruptions are permitted in the case of medical / surgical events or logistical reasons not related to study therapy (e.g., elective surgery, unrelated medical events, participant vacation, and/or holidays). Participants should be placed back on study therapy within 5 weeks of the scheduled interruption, unless otherwise discussed with the Sponsor. The reason for interruption should be documented in the participant's study record.

Dose modifications and delays for eribulin will be allowed and are described below. No re-escalation will be allowed for eribulin. Dose delays for pembrolizumab for adverse events are described below. There are no dose reductions of pembrolizumab allowed. See Section 5.9 for guidelines regarding resumption of pembrolizumab following dose delays.

For toxicities in this Section which are attributable to pembrolizumab alone, only pembrolizumab should be held as directed. It is permissible to continue eribulin despite discontinuation of pembrolizumab in these select cases. This will be left to the treating physician's discretion after discussion and approval of the study PI.

For toxicities in this Section which are attributable to eribulin alone, only eribulin should be held

as directed. It is permissible to continue pembrolizumab despite discontinuation of eribulin in these select cases. This will be left to the treating physician's discretion after discussion and approval by the study PI.

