6.2 Pembrolizumab dosing delays

Participants should be carefully monitored for toxicity. If a treatment delay is required for pembrolizumab, treatment with Eribulin is allowed. Guidelines for dose interruption recommendations for pembrolizumab are shown in Table 4. If treatment with pembrolizumab is withheld permanently, participants are allowed to continue to receive eribulin therapy. Evaluation of possible AEs should occur early, with early withholding of drug, and appropriate treatment as indicated in the management tables and following event specific guidelines. In some cases, pembrolizumab may be resumed as per section 5.9

AEs associated with pembrolizumab exposure may represent an immunologic etiology. These immune-related AEs (irAEs) may occur shortly after the first dose or several months after the last dose of pembrolizumab treatment and may affect more than one body system simultaneously. Therefore, early recognition and initiation of treatment is critical to reduce complications. Based on existing clinical study data, most irAEs were reversible and could be managed with interruptions of pembrolizumab, administration of corticosteroids, and/or other supportive care. For suspected irAEs, ensure adequate evaluation to confirm etiology or exclude other causes. Additional procedures or tests such as bronchoscopy, endoscopy, skin biopsy may be included as part of the evaluation. Based on the severity of irAEs, withhold or permanently discontinue pembrolizumab and administer corticosteroids. Dose interruption and toxicity management guidelines for irAEs associated with pembrolizumab are provided in Table 4.1 to Table 4.9.

Table 4.1 Guidelines for dose interruption and toxicity management guidelines for immune-related AEs associated with pembrolizumab

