General instructions: 
 1. Corticosteroid taper should be initiated upon AE improving to Grade 1 or less and continue to taper over at least 4 weeks. 2. For situations where pembrolizumab has been withheld, pembrolizumab can be resumed after AE has been reduced to Grade 1 or 0 and corticosteroid has been tapered. Pembrolizumab should be permanently discontinued if AE does not resolve within 12 weeks of last dose or corticosteroids cannot be reduced to ≤ 10 mg prednisone or equivalent per day within 12 weeks. 3. For severe and life-threatening irAEs, IV corticosteroid should be initiated first followed by oral steroid. Other immunosuppressive treatment should be initiated if irAEs cannot be controlled by corticosteroids. 				
Immune-related AEs	Toxicity grade or conditions (CTCAEv5.0)	Action taken to pembrolizumab	irAE management with corticosteroid and/or other therapies	Monitor and follow-up
Pneumonitis	Grade 2	Withhold	
 • Administer corticosteroids (initial dose of 1-2 mg/kg prednisone or equivalent) followed by taper 	
 • Monitor participants for signs and symptoms of pneumonitis • Evaluate participants with suspected pneumonitis with radiographic imaging and initiate corticosteroid treatment • Add prophylactic antibiotics for opportunistic infections
	Grade 3 or 4, or recurrent Grade 2	Permanently discontinue		
Diarrhea / Colitis	Grade 2 or 3	Withhold	
 • Administer corticosteroids (initial dose of 1-2 mg/kg prednisone or equivalent) followed by taper 	
 • Monitor participants for signs and symptoms of enterocolitis (ie, diarrhea, abdominal pain, blood or mucus in stool with or without fever) and of bowel perforation (ie, peritoneal signs and ileus). • Participants with \geq Grade 2 diarrhea suspecting colitis should consider GI consultation and performing endoscopy to rule out colitis. • Participants with diarrhea/colitis should be advised to drink liberal quantities of clear fluids. If sufficient oral fluid intake is not feasible, fluid and electrolytes should be substituted via IV infusion.
	Grade 4	Permanently discontinue		

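### After steroid-treated Grade 3 immune-related diarrhea/colitis, Table 4.1 allows pembrolizumab to resume while Sections 5.5 and 5.8 stop it, and the restart pointers in Section 6 cite the wrong section

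*Combined protocol and SAP*

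**What the plan says.** **Stopping rules.** Section 5.5 lists "Grade 3 or Grade 4 drug-related autoimmune or inflammatory events including uveitis, pneumonitis, diarrhea, colitis" among the events that require discontinuation whatever their duration. The items after it deal with other Grade 3 events, laboratory and electrolyte values, and amylase or lipase. None exempts diarrhea or colitis.

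**Restart rules.** Section 5.8 limits Grade 3 restarts to skin rash and thyroiditis and states: "All participants treated with steroids for grade ≥ 3 events should have pembrolizumab discontinued". For hepatitis, pancreatitis, pneumonitis and colitis, it says participants "should resolve to Grade 0 or baseline before retreatment". It also requires a steroid-free interval: "Participants should be off steroids for at least 2 weeks with no recurrence or new events".

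**Toxicity table.** In Section 6.2, Table 4.1 places diarrhea/colitis of Grade 2 or 3 under withhold and keeps permanent discontinuation for Grade 4. The same row directs steroids at 1-2 mg/kg followed by a taper. General instruction 2 then says "pembrolizumab can be resumed after AE has been reduced to Grade 1 or 0 and corticosteroid has been tapered", with 12-week limits on resolution and on steroid reduction.

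**Pointers.** Section 6 says "See Section 5.9 for guidelines regarding resumption of pembrolizumab following dose delays", and the lead-in to Table 4.1 says "In some cases, pembrolizumab may be resumed as per section 5.9". The text after Table 4.9 also sends high-dose steroid management to 5.9. Section 5.9 covers infusion reactions; the restart criteria are in 5.8. The note in Table 4.9 cites 5.10 for infusion reactions, but 5.10 is treatment beyond progression.

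**General text.** Section 1.1 leaves discontinuation after Grade 3 or higher immune-related events to the Principal Investigator's discretion. The gastrointestinal algorithm in Appendix B discontinues immunotherapy at Grade 3-4, but only as the protocol directs.

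**The concern.** Two specific rules give opposite instructions for the same event. A physician managing Grade 3 colitis is likely to work from Table 4.1. That table permits re-exposure once the event has settled and steroids are tapered. Sections 5.5 and 5.8 both end pembrolizumab at that point.

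Section 6 is meant to pass the restart decision to the resumption criteria, which would largely resolve the conflict. The section number is off by one, so a reader who follows it finds guidance on infusion reactions and nothing on restarting after colitis.

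The stake is participant safety and uniform conduct: re-challenge after a serious immune-related event would depend on which page the physician consulted.

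**Working it through.** No design figure is in dispute, so the check is a side-by-side reading followed by a rough size.

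**Step 1. Steroid-treated Grade 3 immune-related diarrhea/colitis.**

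| Source | Instruction |
|---|---|
| 5.5 | Discontinue, any duration |
| 5.8 | Discontinue pembrolizumab (exceptions: thyroiditis, skin rash) |
| 6.2, Table 4.1 | Withhold; may resume at Grade 0-1 after taper |
| 6.2, text after Table 4.9 | Only Grade 3 thyroiditis and skin rash treated like Grade 2 |
| Appendix B | Discontinue, as the protocol directs |
| 1.1 | Principal Investigator's discretion |

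Section 5.5 ends protocol therapy and 5.8 ends pembrolizumab only, but both stop pembrolizumab. The Grade 0 or baseline condition for colitis in 5.8 does not reopen Grade 3: the same section confines Grade 3 restarts to rash and thyroiditis, so the condition is naturally read as applying to Grade 2 colitis.

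**Step 2. Other rows of Table 4.1.** Grade 3 hypophysitis and the Grade 3 row for all other immune-related events may also be withheld rather than stopped, with steroids given. Both meet the same 5.8 rule. Hypophysitis needs a clinical choice, because 5.8 separately lets participants with stable hypopituitarism restart on replacement hormones.

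**Step 3. Restart conditions.**

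| Condition | Table 4.1 | 5.8 |
|---|---|---|
| Grade needed for colitis, pneumonitis, hepatitis | 0 or 1 | 0 or baseline |
| Time off steroids | Taper completed | At least 2 weeks |
| Time limit | 12 weeks | 8 weeks after high-dose steroids |

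The text after Table 4.9 also sets 8 weeks as the longest adverse-event delay.

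**Step 4. Pointers.** Three pointers cite 5.9 where 5.8 is meant: the opening of Section 6, the lead-in to 6.2, and the high-dose steroid sentence after Table 4.9. One cites 5.10 where 5.9 is meant. The reference to 5.9 in 5.3.2 concerns infusion times and is correct.

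**Step 5. Size.** Inputs come from Section 2.6 (combination breast cancer trial) and the planned total of 57.
- Denominator: 24/0.224 = 107.1 and 34/0.318 = 106.9, so n = 107.
- Grade 3-4 diarrhea 4.7%: 0.047 × 107 = 5.03, so 5/107 = 4.67%, Clopper-Pearson 95% CI 1.53% to 10.57%.
- Expected number of 57: 57 × 5/107 = 2.7; limits 57 × 0.0153 = 0.9 and 57 × 0.1057 = 6.0.

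The interval reflects uncertainty in the rate only. The documents do not separate Grade 3 from Grade 4. The all-grade diarrhea figure is 29.9% in both the general list and the possibly immune-related list, so attribution appears not to have been separated.

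**The case against.** The strongest reply is that the protocol contains safeguards. Section 1.1 gives the Principal Investigator discretion over exactly these events. A taper of at least 4 weeks plus 2 weeks off steroids is at least 6 weeks, and 5.5 calls for consulting the PI before restarting after an interruption of more than 5 weeks (that sentence sits in an item on non-drug-related interruptions but is worded generally). Section 5.8 immediately precedes the section cited, and its title names resumption criteria. Appendix B is weak support because it defers to the protocol and grades by CTCAE v4, whereas Table 4.1 uses v5.0.

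Much of this stands, and it makes an unnoticed re-challenge less likely. It does not remove the conflict. A general discretion sentence is a third rule; it does not say whether Table 4.1 or 5.8 prevails. The 2-week steroid-free condition is itself in 5.8, the section the pointers miss.

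A reader might also infer two further conflicts:
- **First Grade 2 pneumonitis needing steroids.** Section 5.5 could be read as stopping treatment, against Table 4.1. The line directly follows the exceptions to the 5-week rule, and the list nesting is lost in the available text, so its level cannot be recovered.
- **Logistical interruption limits** of 8 weeks in 5.8 and 5 weeks in Section 6. Both allow otherwise after discussion with the sponsor, and 5.5 already permits longer non-drug-related gaps with approval. This is not a comparable contradiction.

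**Conclusion.** The plan is wrong as written on this point: it is internally inconsistent. For steroid-treated Grade 3 diarrhea/colitis, Table 4.1 permits what 5.5 and 5.8 deny, and the pointers that should lead to the governing rule are misnumbered. The importance is minor to should-fix.

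About 2.7 of 57 participants (95% CI 0.9 to 6.0) could have Grade 3-4 diarrhea, assuming the breast cancer rates carry over to sarcoma. It would be a mistake to read this as the number re-exposed. Re-exposure also requires an immune-related cause, Grade 3 rather than Grade 4, resolution, a completed taper, no progression and a decision to restart.

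The documents do not show that anyone was re-challenged in this way. Nor do they support any effect on the 12-week endpoint rule, the 19 participants per arm, or power. They do not say whether anyone is still on treatment; long-term follow-up ends with the 15MAY2024 version. If nobody is, the practical use is to check past Grade 3 colitis cases against 5.5 and 5.8.

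**What to change.** 1. **Table 4.1, diarrhea/colitis:** Grade 2 withhold; Grade 3 or 4 permanently discontinue pembrolizumab.
2. **Pointers:** change 5.9 to 5.8 in the opening of Section 6, in the lead-in to 6.2, and in the high-dose steroid sentence after Table 4.9. Change 5.10 to 5.9 in the infusion-reaction note in Table 4.9. Leave 5.3.2 alone, so do not use a global replace.
3. **Table 4.1, general instruction 2:** state that 5.8 governs any restart.
   - Steroid-treated events of Grade 3 or higher discontinue, except thyroiditis and skin rash. This also settles the hypophysitis and all-other Grade 3 rows, unless the clinical team lists them as exceptions.
   - Hepatitis, pancreatitis, pneumonitis and colitis must return to Grade 0 or baseline.
   - At least 2 weeks off steroids, apart from replacement doses.
   - The 8-week limit replaces 12 weeks.
4. **Section 1.1:** make the discretion sentence subject to 5.5 and 5.8. Otherwise the conflict survives the amendment.

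The cost is one consistency amendment and a notice to treating investigators. No procedures are added and no design figure changes. The downside is that a few participants lose a re-challenge option, which 5.5 and 5.8 already deny for Grade 3 colitis.
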